### **Hypotensive Event Measurement:**

Hypotension Definition: MAP <65 mmHg for more than 1 minute. In Group CM, hypotension will be measured by conventional non-invasive blood pressure cuff. In Group HPI hypotension will be measured by ClearSight.

In typical clinical ELA settings, the following definition for hypotension is used to guide BP treatment: drop in systolic blood pressure (SBP) >20% from baseline, or systolic blood pressure <100 mmHg, or, if there are any fetal heart rate concerns. These parameters will continue per existing clinical standards and are expected to be evenly randomly distributed between the two groups by virtue of randomization. The Group HPI treatment protocol adds to the Conventional monitoring protocol as the ClearSight monitor and monitoring algorithm more clearly delineate types of hypotensive events.

In Group HPI we used an index threshold for treatment that builds upon findings from Maheshwari et al. In their pilot randomized trial of 214 noncardiac surgical patients, 105 (49%) patients randomized to management with a hypotension prediction algorithm, intraoperative hypotension was not reduced compared with controls. They suggested that a lower alert threshold enabling adequate warning time, and a simpler treatment algorithm that emphasizes prompt treatment after alert may help. Therefore, our HPI alert threshold for treatment is specified at 75 (on the monitor/ClearSight algorithm) and the treatment algorithm, specified below, was made as simple as possible.

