**e. Protocol specific methods:**

Patients will be screened electronically using the electronic health record upon arrival at the Womancare birth center at UPMC Magee. Patients are eligible if they are pregnant, admitted for labor and delivery, and receiving ELA. If patients are undecided about whether they will receive ELA but are interested in the research, they may be consented and then marked as a "screen failure" if they do not receive ELA. These patients will not be randomized. Patients who receive ELA will be randomized to treatment of hypotension according to conventional monitoring (Group CM) or monitoring by HPI (Group HPI). Randomization will be 1:1 and occurs immediately after informed consent and signature for research activities. Subjects will be informed of their assignment after all research activities and data collection have been completed. Total monitoring time will be 4 hours starting from the initiation of ELA. To enable group comparisons of total time in hypotension, all participants will wear ClearSight and a Conventional Monitoring cuff; Group CM will be blinded to ClearSight output and receive standard care for the treatment of hypotensive events post-epidural-labor analgesia. Group HPI will receive treatment of hypotension according to ClearSight output and specified by the hypotension treatment protocol below.

Clinical research staff who have been trained in ClearSight will apply the device and troubleshoot any problems. Providers will be trained on the monitor, its interpretation, and output, prior to study launch and real time at the time of active study participant enrollment. This training applies only to those participants who will receive non-blinded treatment assignment

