## **ELA Protocol: Combined Spinal Epidural (CSE) Analgesia**

A baseline blood pressure will be recorded immediately prior to the initiation of ELA.

At patient request, an experienced anesthesia provider will perform procedure to place ELA using CSE technique in the sitting position. CSE is chosen due to reliability and rapidity with which hypotension can be predicted within the ELA encounter. A meta-analysis of studies comparing low-dose epidural analgesia with CSE analgesia found no difference in the incidence of hypotension between the two techniques.

The epidural space will be found using loss of resistance to saline. A 25-27g Sprotte needle will be introduced to the subarachnoid space. After confirmation of cerebrospinal fluid (CSF), a spinal dose of 15mcg fentanyl and 2.5mg bupivacaine will be given (this action defines T0 = initiation of CSE). At T0 blood pressure monitoring and data recordings will begin per protocol specified below.

A 19-20g flexible epidural catheter will then be introduced and threaded 5-6cm in the epidural space. Test dose will be delivered through the epidural catheter and will consist of lidocaine 1.5% with epinephrine, 3mL. The anesthesia clinician will declare positive or negative test dose 5 min after administration of test dose. A positive test dose will result in withdrawal from the study.

Maintenance of ELA will be by patient-controlled epidural analgesia using programmed intermittent epidural bolus (PIEB) at our institutional standards: Ropivacaine 0.1% +2mcg/mL fentanyl, 8mL q40min, 8mL demand q8min, maximum hourly volume 24mL. (Smiths CADD®-Solis Infusion System, Infusion Pump, ICU Medical, Dublin, OH). The first PIEB dose is delivered 40 minutes after the initiation of the pump.

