### \*\*Hypotension as defined above

**Key:** **MAP:** mean arterial pressure; **CM:** conventional monitoring (standard care); **HPI:** hypotensive prediction index group (ClearSight device and algorithm); **BP:** blood pressure; **SBP:** systolic blood pressure; **NIBP:** non-invasive blood pressure; **IVP:** Intravenous push

e. **Electronic Health Record Variables Collected:**

- Age
- Race/Ethnicity
- Insurance status
- Gravidity
- Parity
- Estimated gestational age
- Body mass index
- Induction vs Spontaneous Labor
- Last known cervical exam at the time of ELA initiation
- Pain score immediately prior to ELA initiation
- Total vasopressor doses from time of ELA initiation until delivery
- Time of hypotensive event start to time of treatment for hypotension
- Changes in fetal heart rate Yes/No
  - If Yes: Time, in minutes, from ELA initiation until category change detected
- Presence or absence of fetal heart rate decelerations within 1 hour of initiation of ELA (yes/no)
- Mode of delivery
- Neonatal weight
- Neonatal Apgar scores
- Neonatal cord blood pH

3. **Risks/Benefits:**

Benefits

Close monitoring and treatment of hypotension

Risks

Loss of confidentiality

Discomfort with devices

Inconvenience answering questions

Risk of obtaining a false positive reading and being given fluids or other management of blood pressure that was not necessary.

4. **Data Analysis:**

a. **Data collection form:** See Appendix

b. **Statistical Analysis Plan**

Descriptive statistics will be calculated for variables and compared between groups. We will report mean  $\pm$  SD for normally distributed continuous data; median (interquartile range) for data not normally distributed or for data with outliers or ordinal data; and number (percentage) for categorical data. Kolmogorov–Smirnov test will be applied to test for normality of data distribution. An unpaired two-tailed t test will be used for comparing parametric data between groups, and Mann–Whitney U and Wilcoxon rank sum tests will be used for nonparametric data. The chi-square test or Fisher exact test will be applied as appropriate for comparing proportions between groups.  $P < 0.05$  will be considered statistically significant.

*Primary Outcome Analysis (Survival Analysis)*

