Single-variable proportional hazards regression models will be created for each potential covariate of interest. Time-to-event estimates  $+$ /SE for both groups will be calculated from the single-variable models. Using  $P < 0.10$  from the univariate models as a threshold for inclusion in the multivariable model, the best-fit multivariable model will then be generated by removing variables with  $P > 0.05$  from the multivariable model in a backward stepwise fashion. To assess the primary outcome regarding relationship between treatment groups and “survival” (treatment-free) time, a proportional hazards model will be used to assess the effect of the monitoring type, with effects of covariates controlled in the best-fit multivariable model.

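### Time-to-treatment has no stated common start: hypotension is timed by cuff in Group CM and by ClearSight in Group HPI, and the survival model names no origin

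*Combined protocol and SAP*

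**What the plan says.** - Sections III.2.a and III.2.c list time-to-treatment, in minutes, among the primary outcomes. Neither gives a start point.
- *Hypotensive Event Measurement* defines hypotension as MAP under 65 mmHg lasting over 1 minute, then assigns the device by group: "In Group CM, hypotension will be measured by conventional non-invasive blood pressure cuff. In Group HPI hypotension will be measured by ClearSight".
- *BP Monitoring Protocol* cycles the CM cuff every 3 min for 30 min and every 15 min after that. ClearSight runs continuously in Group HPI.
- *Electronic Health Record Variables Collected* lists "Time of hypotensive event start to time of treatment for hypotension" and names no device.
- *Primary Outcome Analysis (Survival Analysis)* describes the outcome as survival time ("treatment-free) time, a proportional hazards model will be used to assess the effect of the monitoring type"), with no origin and no censoring rule.
- *Protocol specific methods* (III.2.e) puts both devices on everyone, for a different outcome: "To enable group comparisons of total time in hypotension, all participants will wear ClearSight and a Conventional Monitoring cuff". CM is blinded to the ClearSight output. The same section says "Total monitoring time will be 4 hours starting from the initiation of ELA".
- *ELA Protocol* says "At T0 blood pressure monitoring and data recordings will begin per protocol specified below" and ties T0 to the spinal dose ("this action defines T0 = initiation of CSE"). *BP Monitoring Protocol* ties T0 to the test dose.
- *Hypotension Treatment Protocol* lets treatment in Group HPI follow either an alert or an episode. The usual systolic and fetal heart rate criteria continue in both groups.

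**The concern.** The Background names delayed recognition under intermittent checks as the problem, and the hypothesis is that HPI shortens time-to-treatment. If event start is read off each group's own device, the control clock does not start until the cuff has found the low pressure. The delay of interest then drops out of the control arm, while the HPI arm is timed from continuously observed onset. A CM episode that falls between cuff readings starts no clock at all.

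Treatment on an HPI alert is a second problem, whichever origin is used. On an onset clock it gives a negative time, or no time at all if hypotension is averted. On a T0 clock it counts as early treatment even in a patient who would never have become hypotensive.

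Section III.2.a wants the pilot to estimate the difference for a continued study. If the interval means different things in the two arms, that problem carries into the next trial's planning.

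**Working it through.** **The plan's own figures.** Expected events: 30 × 0.20 = 6, as III.2.b states. Cuff readings in the first 30 min: 30 / 3 = 10, as *BP Monitoring Protocol* states. The plan gives no power calculation for this outcome.

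**Uncounted CM wait if event start is the first low cuff reading.** Inputs: cuff interval I = 3 or 15 min (*BP Monitoring Protocol*). Assumptions: onset is uniform within an interval, and one low reading counts as an event. For an episode of d min, P(caught) = min(d/I, 1), and mean wait if caught = min(d, I)/2.

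| I (min) | d (min) | P(caught) | mean uncounted wait (min) |
|---|---|---|---|
| 3 | 3 or more | 1 | 3/2 = 1.5 |
| 15 | 15 or more | 1 | 15/2 = 7.5 |
| 15 | 10 | 10/15 = 0.67 | 10/2 = 5.0 |
| 15 | 5 | 5/15 = 0.33 | 5/2 = 2.5 |

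Simulation gave the same values to rounding.

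**Mix of early and late onsets.** For episodes of 15 min or more, with a share f of onsets in the first 30 min, the mean is 1.5f + 7.5(1 − f). That gives 1.5, 2.1, 3.0 and 4.5 min at f = 1, 0.9, 0.75 and 0.5. The plan does not give f. Its reason for the technique ("CSE is chosen due to reliability and rapidity with which hypotension can be predicted within the ELA encounter") favours the low end.

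**Treatment on other criteria.** Suppose a share s of CM episodes is treated on systolic or fetal criteria with no uncounted wait (assumption). The means become (1 − s) × 1.5 and (1 − s) × 7.5. At s = 0.25 they are 1.1 and 5.6 min; at s = 0.5 they are 0.75 and 3.75 min.

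**If one reading is not enough.** A single cuff reading cannot show that MAP stayed low for over 1 minute. If two consecutive low readings are required, a 5-min episode is caught (5 − 3)/3 = 67% of the time at 3-min cycling and never at 15-min cycling.

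**Alert treatment on an onset clock.** The Background cites warning leads of 5, 10 and 15 min. With an assumed 2-min response, onset-to-treatment is 2 − 5 = −3, 2 − 10 = −8 and 2 − 15 = −13 min. If treatment prevents the episode, no onset exists. A standard proportional hazards model timed from onset accepts neither, and the plan does not say how to handle them.

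**The case against.** The strongest reply is that a common origin already exists. Recording begins at T0 in both arms, the window runs 4 hours from initiation, and treatment-free survival time reads naturally as time from T0. The health-record list may only describe data to be collected, and the device rule may only name what guides care. This reply stands in part: T0 could serve, so it would be wrong to infer that no valid common clock is available. But the plan never assigns T0 to this outcome. The one interval it spells out starts at the hypotensive event, and the device rule appears under a heading about measuring events. The two T0 anchors apply to both arms alike, so they need reconciling but are not themselves a source of arm-dependent timing.

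The data collection form is not reproduced in the text available. It may define event start; if so, the SAP should carry that definition.

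A reader might also infer that the rule biases the trial against HPI, or even reverses the result. With an assumed 2-min response in both arms and a 1-min confirmation in HPI, separate clocks give CM 2.0 and HPI 3.0 min. A common ClearSight clock gives CM 3.5 or 9.5 min (2 + 1.5 or 2 + 7.5) against HPI 3.0 min. The documents do not support a claim of reversal: the response time is assumed, and alert treatment can favour HPI.

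Finally, this is a pilot of 30 that is not expected to show a difference, and total time in hypotension is already planned. Both points limit the consequences but do not define the primary interval.

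**Conclusion.** The concern holds as a fault in the definition of one primary outcome, and it should be fixed before analysis. Followed as written, an arm-specific device rule combined with timing from event start omits a mean CM wait of 1.5 min in the 3-min phase and 7.5 min in the 15-min phase. Both figures assume uniform onset, one low reading as the event, and an episode lasting at least one cuff interval. The average over a real mix of episodes is unknown and probably nearer the low end if most onsets are early. Short CM episodes can be missed entirely.

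The net direction is uncertain: the uncounted wait tends to hide an HPI benefit, while alert treatment can create an apparent one. What can be said is that the pilot's estimated difference would not compare like with like. The ease and feasibility outcomes are untouched.

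**What to change.** These changes concern outcome measurement only; care and CM blinding stay as they are.

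1. Before analysis, name one origin for both groups, for the collected variable and for the survival model. For onset-based time, date onset in both groups from the stored ClearSight trace, not by cuff in CM: the start of the first run of MAP under 65 mmHg lasting over 1 minute, with later runs dated the same way.
2. Analyse by episode. Link a treatment only to the episode in progress. Treat an episode that resolves untreated as ended untreated at resolution, and report the number of these by group. Otherwise a CM patient with an unseen dip at 35 min and treatment for a separate episode at 180 min would score 180 − 35 = 145 min, which would favour HPI. Allow for repeated episodes within a patient.
3. Report treatment before onset, or without any onset, by group and by trigger (alert, systolic pressure, fetal heart rate). Beside it, in all randomised patients, report time from T0 to first treatment and the already planned total ClearSight time with MAP under 65 mmHg.
4. Specify or record which arm carries ClearSight relative to the cuff in Group CM. *Pre-ELA Protocol* requires the same arm only in Group HPI, while citing 10 mmHg differences between arms. An offset of that size could shift or create onsets at a 65 mmHg threshold.
5. Reconcile the T0 definitions in *ELA Protocol* and *BP Monitoring Protocol*.

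The cost is SAP wording, extraction of the ClearSight trace, and matching its time stamps to charted treatment times. No new device is needed. Limits remain: gaps in the trace must be flagged, events will be few, and the onset-based comparison covers only patients who reach MAP under 65 mmHg, a group formed after randomisation. That last limit is why item 3 asks for results in all randomised patients.

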### ***Blood Pressure Monitoring and Hypotension treatment protocol is standardized as below.***

#### **BP MONITORING PROTOCOL**

Group CM	Group HPI
-----------------	------------------

<math>T_0</math> At the time of test dose delivery, automated NIBP cycles will begin q3min for 30 minutes, amounting to a total of at least 10 blood pressure measurements.
 
<math>T_{30}</math> After 30 minutes, NIBP cycles to q15min per existing clinical standards
 
<math>T_{4\text{hours}}</math> Monitoring for research ends
	
<math>T_0</math> At the time of test dose delivery, Clearsight monitoring continues.
 
<math>T_0 - T_{4\text{hours}}</math> ClearSight monitoring is continuous
 
<math>T_{4\text{hours}}</math> Monitoring for research ends

--	--

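### T0 is the spinal dose in the CSE section but the later test dose in the blood pressure monitoring table, so the start of scheduled cuff cycling and the 30-minute and 4-hour marks are not fixed

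*Combined protocol and SAP*

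**What the plan says.** The section on combined spinal epidural analgesia gives an explicit definition. On giving the spinal fentanyl and bupivacaine it says "this action defines T0 = initiation of CSE", and then "At T0 blood pressure monitoring and data recordings will begin per protocol specified below". The next step is "A 19-20g flexible epidural catheter will then be introduced and threaded 5-6cm in the epidural space", and the test dose is given through that catheter.

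The BP MONITORING PROTOCOL table is what that section defers to, and it is the only cuff schedule in the document. It labels T0 as test-dose delivery in both columns:

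- Group CM: "At the time of test dose delivery, automated NIBP cycles will begin q3min for 30 minutes", then every 15 minutes from T30, with research monitoring ending at T4hours.
- Group HPI: "At the time of test dose delivery, Clearsight monitoring continues", and monitoring is continuous to T4hours.

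Under Protocol specific methods, the follow-up clock is "Total monitoring time will be 4 hours starting from the initiation of ELA". Since ELA is placed by CSE, this fits the spinal dose and not the test dose.

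**The concern.** The two definitions cannot both be followed. The spinal dose and the test dose are separated by catheter placement, and the protocol does not say how long that takes. Staff working from the table would begin the 3-minute cuff cycle only after the catheter is in. Group CM would then have no scheduled cuff cycle in the minutes just after the intrathecal dose. The 3-minute block and the 4-hour end would both run late against the ELA-initiation clock.

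Time-to-treatment of hypotension is a primary outcome, and in Group CM hypotension is measured by cuff (Hypotensive Event Measurement). Group CM also wears ClearSight, but its output is blinded and cannot prompt treatment. When scheduled cuff readings start therefore bears on when a Group CM event can be picked up. The pilot is also meant to yield an estimate for continuing the study (Size of study groups), so its schedule may be reused.

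**Working it through.** **The plan's own figure.** The table promises at least 10 readings in the first block: 30 min / 3 min = 10, or 11 counting a reading at time 0. This reproduces and does not depend on which T0 is used. Only the position of the block changes.

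**Order of events.** Spinal dose, then catheter, then test dose through the catheter. Call the gap from spinal dose to test dose g. The document does not give g, so the values below are assumptions. Under the table, the 3-minute block runs from g to 30 + g minutes after the spinal dose, and research monitoring ends at 240 + g. For g = 5 that is 5 to 35 minutes and 245 minutes, a shift of 5/240 = 2.1%, equal in both arms. Readings at 0 and 3 minutes would not be taken: 2 readings, or 1 if the time-0 reading is not counted.

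**Detection delay in Group CM.** Assume onset is uniform over the first H minutes after the spinal dose, with cuff readings at g, g+3, g+6 and so on until detection. Two detection rules are used: the first reading after onset, or the first reading at least 1 minute after onset (an approximation to the more-than-1-minute definition). Mean wait from onset to the detecting reading, H = 15:

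| g (min, assumed) | First-reading rule | Added | 1-minute rule | Added |
|---|---|---|---|---|
| 0 to 3 | 1.50 | 0 | 2.50 | 0 |
| 4 | 1.70 | 0.20 | 2.50 | 0 |
| 5 | 1.90 | 0.40 | 2.70 | 0.20 |

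Check for g = 5:

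- First-reading rule: (12.5 + 3 × 4.5 + 2.5)/15 = 28.5/15 = 1.90. The 12.5 comes from onsets in the 5-minute gap (5²/2), each 4.5 from a full 3-minute cycle (3²/2), and 2.5 from the last part-cycle.
- 1-minute rule: (12 + 3 × 7.5 + 6)/15 = 40.5/15 = 2.70.

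With H = 30 and g = 5 the means are 1.70 and 2.60, so 0.20 and 0.10 minutes are added. The longest possible wait with a 5-minute gap rises from 3 to 5 minutes (first-reading rule) or from 4 to 5 (1-minute rule).

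The result is sensitive to g. At g = 10 and H = 15 the first-reading mean is (50 + 4.5 + 4)/15 = 3.90, an added 2.4 minutes; under the 1-minute rule 1.8 minutes are added.

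**How many events could be affected.** The protocol predicts 6 events in 30 patients (20%). With 1:1 allocation about 3 fall in Group CM. The expected number starting in a 5-minute gap is 3 × 5/H: 1.0 for H = 15, 0.5 for H = 30, and 0.06 if onset is spread over all 240 minutes.

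**The case against.** The strongest reply is that the CSE section already settles the matter. It uses defining words and says, without separating the arms, that monitoring and recording begin at the spinal dose. The table cell is then a slip that a trained site would read past. That is probably what was intended, but the same sentence hands the schedule to the table, and the table says otherwise. The intention supports correcting the table and does not make the two texts agree.

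The reply is right on consequence. Before the spinal dose, "A baseline blood pressure will be recorded immediately prior to the initiation of ELA". The cuff is already on the arm, an experienced anesthesia provider is performing the procedure, and the usual clinical treatment triggers continue. What the literal table lacks is a scheduled cuff cycle, not monitoring.

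A reader might go further in three directions that the documents do not support:

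- **A built-in bias between arms.** This rests on one pair of verbs: cuff cycling begins in Group CM, while ClearSight continues in Group HPI. The second may mean only that the device is switched on. The protocol does not say whether HPI alerts are acted on before the test dose.
- **A wrong origin for the primary survival model.** The Primary Outcome Analysis names no origin, and the collected time-to-treatment variable runs from event start to treatment. If event start in Group CM is stamped from the cuff, the recorded Group CM time would not change at all. Which origin the model should use is a separate question that the T0 label does not decide.
- **Distorted fetal and vasopressor variables.** Those variables are anchored in words to ELA initiation and do not use T30 or T4hours.

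**Conclusion.** The contradiction is certain from the text: two events carry the label T0, one necessarily later than the other, and no passage reconciles them. Followed literally, the table delays scheduled cuff cycling in Group CM until after catheter placement and moves the 30-minute and 4-hour marks by the same unstated gap. That the delay falls on Group CM detection alone is suggested but not established.

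For assumed gaps up to 5 minutes the added mean delay is 0 to 0.4 minutes, and it is 0 for gaps up to 3 minutes. That zero is an average under uniform onset and does not hold for every patient: with onset at 2.5 minutes, detection comes at 3 minutes if g = 0 but at 5 minutes if g = 2. A longer gap would cost more.

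No confirmatory conclusion depends on this, because the protocol does not expect 30 patients to show a difference. Wrong as written, minor.

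**What to change.** In both columns of the BP MONITORING PROTOCOL table, replace test-dose delivery with the spinal dose (initiation of CSE) as T0. Record its time. Start the Group CM 3-minute cuff cycle and ClearSight recording in both arms at that moment, and count T30 and T4hours from it. If the sponsor wants 3-minute cycling to last until 30 minutes after the test dose, lengthen the block and do not move its start.

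The cost is one corrected table entry in each column and one time stamp per patient. No readings are added if the 30-minute block simply starts earlier. Lengthening it adds at most 2 automated readings for a gap up to 5 minutes; the exact number depends on how the end points are counted. Sample size and the planned tests are unaffected.
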